2.1 PROTOCOL SYNOPSIS

The Protocol Synopsis is in [Appendix 1](#). For additional details, see the Schedule of Assessments in [Appendix 2](#).

2.2 ENDPOINTS

All endpoints will be measured and described separately for the inhibitor and non-inhibitor cohorts. For all endpoints in this section, BPA use is specific for patients with inhibitors and FVIII use is specific for patients without inhibitors.

2.2.1 Primary Efficacy Endpoints

- Percentage of patients without excessive bleeding at surgical sites and did not require BPA/FVIII use for bleeding related to the surgery, from the start of the surgery until the patient is discharged from the surgery. For the purposes of this endpoint, the absence of excessive bleeding and BPA/FVIII use will be measured by a good to excellent rating using the hemostatic efficacy scale (ISTH SSC recommendations, see References) and will be determined upon patient discharge by the healthcare professional performing the procedure.

- Percentage of patients with excessive bleeding at surgical sites and required BPA/*FVIII* use for bleeding related to the surgery, from the start of the surgery until the patient is discharged from the surgery. Bleeding and BPA/*FVIII* use will be assessed using the hemostatic efficacy scale and measured by a rating of fair to poor, and will be determined upon patient discharge by the healthcare professional performing the procedure.
 - Dose and schedule (including number of doses, total dose, and frequency) of BPAs/*FVIII* used per bleed for excessive bleeding at surgical sites will be summarized.

- Percentage of patients who, after being discharged from surgery, experienced bleeds that were either related or unrelated to the surgery and also required BPA/*FVIII* use
 - Dose and schedule (including number of doses, total dose, and frequency) of BPAs/*FVIII* used per bleed will be summarized.

Bleeding events and self-administered BPA/*FVIII* use in the third endpoint above are self-reported on the Bleeding and Medication Diary CRF page by patients who undergo the surgical procedure in the study. BPA/*FVIII*, whenever administered by the health care provider, will be obtained and reported by the PI on the Concomitant Medication CRF page.

2.2.2 Secondary Efficacy Endpoints

Not applicable.

2.2.3 Exploratory Efficacy Endpoints

- In the original protocol, select efficacy endpoints were to be summarized descriptively by plasma emicizumab concentration levels. Given that this study is being terminated early with limited sample sizes, these will no longer be performed.
- Percentage of patients with zero bleeds (regardless of treated or not) after being discharged from surgery.

2.2.4 Pharmacokinetic Endpoints

- Emicizumab plasma concentrations on the day of the surgery will be summarized descriptively.

2.2.5 Safety Endpoints

- Incidence and severity of all adverse events
 Incidence and severity of serious adverse events
 Incidence and severity of adverse events of special interest

- Percentage of patients with surgical complications requiring hospitalization or return to surgery
- Percentage of patients who need blood/blood product transfusions (i.e., platelets, plasma, etc.) during surgery
- In the original protocol, selected safety endpoints were to be descriptively summarized by plasma emicizumab concentration levels. Given the early termination of this study and limited sample sizes, these will no longer be performed.

2.3 DETERMINATION OF SAMPLE SIZE

The sample size for this study is based on clinical rather than statistical considerations, taking into account the limited number of patients with a planned minor surgery available for participation in this study. Table 5 illustrates the precision of this study for a binary efficacy endpoint assuming a total of approximately 20-30 patients per cohort enrolled into this study, receiving emicizumab, and undergoing a protocol-specified minor surgery.

During the study, a re-assessment of the initially specified sample size was allowed but never needed to be performed.

Table 1 Precision of the Study for a Binary Efficacy Endpoint (Illustrative Purposes)

Sample Size	Count of Events ^a	Estimate of Proportion	Lower Limit of 95% CI ^b	Upper Limit of 95% CI ^b
20	2	0.1	0.012	0.317
20	6	0.3	0.119	0.543
20	10	0.5	0.272	0.728
30	3	0.1	0.021	0.265
30	9	0.3	0.147	0.494
30	15	0.5	0.313	0.687

^a This is the assumed observed count of events of interest.

^b Calculated using exact test procedure based on the Clopper-Pearson method (Clopper et al. 1934).

2.4 ANALYSIS TIMING

Only one analysis is planned at the end of the study after the database is cleaned and locked.

3. STUDY CONDUCT

Patients are considered to be enrolled into the study once they sign the informed consent form. Safety follow-up will be conducted after the informed consent form is signed.

3.1 RANDOMIZATION ISSUES

Not applicable.

3.2 INDEPENDENT REVIEW FACILITY

Not applicable.

3.3 DATA MONITORING

Not applicable.

4. STATISTICAL METHODS

This is an open-label, single-arm, multicenter study. No statistical hypothesis will be tested.

Only descriptive summaries will be presented for data collected in this study and the data will be summarized separately for the inhibitor and non-inhibitor cohorts. Continuous variables will be summarized using means, standard deviations, medians, and ranges; categorical variables will be summarized using proportions, and 95% confidence intervals, where applicable. In the event that sample sizes are too small or data too sparse given the early termination of this study, summaries will be relegated to simple listings.

4.1 ANALYSIS POPULATIONS

4.1.1 All Enrolled Population

All patients who sign informed consent.

4.1.2 Efficacy Analysis Population

All enrolled patients who receive emicizumab and undergo a minor surgery.

4.2 ANALYSIS OF STUDY CONDUCT

The number of patients who enroll, discontinue, or complete the study will be analyzed separately for each inhibitor and non-inhibitor cohort and will be summarized overall and by type of surgery for the all enrolled population. Reasons for premature study withdrawal will be listed and summarized. Enrollment and major protocol deviations will be listed and evaluated for their potential effects on the interpretation of study results.

4.3 ANALYSIS OF DEMOGRAPHICS, BASELINE CHARACTERISTICS, AND MEDICAL HISTORY

Demographic, baseline characteristics, and medical history will be summarized using means, standard deviations, medians, and ranges for continuous variables and proportions for categorical variables, as appropriate. Summaries will be presented separately for the inhibitor and non-inhibitor cohorts and will be displayed overall and by type of surgery for the all enrolled population.

4.4 EFFICACY ANALYSIS

Descriptive statistics along with 95% Clopper Pearson confidence intervals will be used to provide point estimates and precision related to efficacy outcomes. All efficacy analyses will be performed on the efficacy analysis population.

4.4.1 Primary Efficacy Endpoint

The first 2 primary endpoints listed under section 2.2.1 are composite endpoints from data points collected on the “On-study Targeted Surgery and Procedure Log” CRF page: “Intraoperative and/or postoperative blood loss increased over expectation for the non-hemophilic patient determined at the time of discharge” and “Did the patient use any BPA/*FVIII* for the surgery before the discharge?”.

Primary endpoint 1 is met when response to “Intraoperative and/or postoperative blood loss increased over expectation for the non-hemophilic patient determined at the time of discharge” is “0 to <10%” or “10% to < 25%” AND response to “Did the patient use any BPA/*FVIII* for the surgery before the discharge?” is “No”.

Primary endpoint 2 is met when response to “Intraoperative and/or postoperative blood loss increased over expectation for the non-hemophilic patient determined at the time of discharge” is “25% to <50%” or “>=50%” AND response to “Did the patient use any BPA/*FVIII* for the surgery before the discharge?” is “Yes”.

For the purposes of summarizing the dose and schedule of BPA use per bleed as it relates to primary endpoint 2, BPAs/*FVIII* used for excessive bleeding at surgical sites are reported by the investigator and captured in “Concomitant Medications” CRF.

Primary endpoint 3 is also a composite endpoint based on information collected in “Bleed and Medication Diary” and “Concomitant Medications” CRFs.

For primary endpoint 3, bleeding information is self-reported by patients (or patient’s legally authorized representative) on the “Bleed and Medication Diary” and transcribed into the “Bleed and Medication Diary” CRF page. BPAs/*FVIII* used to treat excessive bleeding are also self-reported by patients if they are administered by the patients. BPAs/*FVIII* administered by the investigators to treat the bleeding will be reported on the “Concomitant Medications” CRF page.

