**Table 1 Objectives and Endpoints**

Primary Objective	Corresponding Endpoints

 
To evaluate the efficacy of emicizumab in preventing surgery-related bleeding in PwHA with and without inhibitors undergoing minor surgical procedures
 
	
Efficacy will be measured by:
 
 
Percentage of patients without excessive bleeding at surgical sites and did not require BPA/FVIIIa use for bleeding related to the surgery, from the start of the surgery until the patient is discharged from the surgery. For the purposes of this endpoint, the absence of excessive bleeding and BPA/FVIIIa use will be measured by a good to excellent rating using the hemostatic efficacy scale (ISTH SSC recommendations, see Appendix 2) and will be determined upon patient discharge by the healthcare professional performing the procedure.
 
Percentage of patients with excessive bleeding at surgical sites and required BPA/FVIIIa use for bleeding related to the surgery, from the start of the surgery until the patient is discharged from the surgery. Bleeding and BPA/FVIIIa use will be assessed using the hemostatic efficacy scale and measured by a rating of fair to poor, and will be determined upon patient discharge by the healthcare professional performing the procedure.               
 
Dose and schedule (including number of doses, total dose, and frequency) of BPAs/FVIIIa used per bleed for excessive bleeding at surgical sites will be summarized.
 
 
 
Percentage of patients who, after being discharged from surgery, experienced bleeds that were either related or unrelated to the surgery and also required BPA/FVIIIa use               
 
Dose and schedule (including number of doses, total dose, and frequency) of BPAs/FVIIIa used per bleed will be summarized
 
 
 

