### Assessment of Hemostatic Response for Surgical Procedures

Excellent	Intraoperative and postoperative blood loss similar (within 10%) to the non-hemophilic patient with no extra (unplanned) doses of FVIII/FIX/'bypassing agents' needed and blood component transfusions are similar to the non-hemophilic patient
Good	Intraoperative and/or postoperative blood loss slightly increased over expectation for the non-hemophilic patient (between 10 and 25% of expected), but the difference is judged by the involved surgeon/anesthetist/relevant healthcare professional to be clinically insignificant as evidenced by no extra (unplanned) doses of FVIII/FIX/'bypassing agents' needed and blood component transfusions are similar to the non-hemophilic patient
Fair	Intraoperative and/or postoperative blood loss increased over expectation (25-50%) for the non-hemophilic patient and additional treatment is needed such as extra (unplanned) doses of FVIII/FIX/'bypassing agents' or increased blood component use (within two-fold) of the anticipated transfusion requirement
Poor	Significant intraoperative and/or postoperative blood loss that is substantially increased over expectation (> 50%) for the non-hemophilic patient, requires intervention, and is not explained by a surgical/medical issue other than hemophilia, unexpected hypotension or unexpected transfer to an Intensive Care Unit due to bleeding or substantially increased blood component use (> 2 fold) of the anticipated transfusion requirement

Source: Blanchette et al. 2014.

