2. STUDY DESIGN

This Phase IV, multicenter study will evaluate whether PwHA receiving emicizumab prophylaxis can safely undergo minor surgical procedures without additional prophylaxis with BPAs for patients with inhibitors or FVIII for patients without inhibitors. Current guidelines recommend a pre-operative dose of BPA/FVIII as surgical prophylaxis, but in patients on emicizumab prophylaxis in this study, additional pre-operative prophylaxis with BPA/FVIII will not be used. The use of BPA/FVIII for excessive surgical bleeding will be measured intraoperatively and postoperatively. In addition, surgical complications from bleeding and blood product transfusions will be evaluated. This study will assess emicizumab prophylaxis alone to control surgery-related bleeding in PwHA undergoing minor surgical procedures.

[figure not shown]
Patients can be screened and enrolled up to 60 days prior to surgery. They must have received a minimum of four loading doses of emicizumab prior to their surgical procedure, been adherent with emicizumab prophylaxis, and must not have received BPA/FVIII for at least 24 hours prior to surgery. In addition, they must plan to continue emicizumab prophylaxis for at least 1 month after the surgical procedure. Follow-up will be conducted by phone on Study Days 2 and 3 (approximately 24 and 48 hours post operation) to record any BPA/FVIII use and surgical bleeding within the first 48 hours, as well as treatment of any other bleeding unrelated to surgery. BPA/FVIII should only be used for treatment of bleeding. Follow-up will be conducted in person on Study Day 8 (± 2 days) to examine the patient for any postsurgical complications and to collect information on treatment of bleeding. Lastly, follow-up will be conducted by phone on Study Day 28 (± 2 days) to record any surgical complications, bleeds, and/or use of BPA/FVIII (see Appendix 2).

Blood samples will also be collected in this study for observational purposes and will not be used to determine eligibility or treatment decisions. Samples will be used to evaluate emicizumab concentration (PK) prior to surgery.

Safety follow-up will be conducted after signing the informed consent form and patients will be monitored for adverse events as noted above to evaluate the safety of emicizumab alone or in combination with BPA/FVIII.

Figure 1 shows the study schema.

Figure 1 Study Schema

FVIII= factor VIII; US= United States.

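### Primary endpoint 2 is said to be measured by a Fair or Poor rating, but the SAP codes it as at least 25% excess blood loss and BPA/FVIII use, which can miss Fair/Poor patients and leaves two different outcomes unreported

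*SAP*

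**What the plan says.** SAP 2.2.1 defines endpoint 2 in two sentences. The first gives a conjunction: "Percentage of patients with excessive bleeding at surgical sites and required BPA/*FVIII* use for bleeding related to the surgery", from the start of surgery to discharge. The second says how it is measured: bleeding and BPA/FVIII "use will be assessed using the hemostatic efficacy scale and measured by a rating of fair to poor". Protocol Table 1 has the same pair, with the endpoint "measured by a rating of fair to poor, and will be determined upon patient discharge by the healthcare professional performing the procedure".

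The scale is in Protocol Appendix 2:

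- Excellent and Good require "no extra (unplanned) doses of" factor or bypassing agent, and blood component use similar to that of a non-hemophilic patient.
- Fair is 25–50% loss over expectation plus additional treatment. That treatment may be extra factor or bypassing doses "or increased blood component use (within two-fold) of the anticipated transfusion requirement".
- Poor is loss more than 50% over expectation that "requires intervention, and is not explained by a surgical/medical issue other than hemophilia". It also names unexpected hypotension, unexpected ICU transfer and more than two-fold blood component use. It does not name BPA/FVIII.

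SAP 4.4.1 builds endpoints 1 and 2 from two items on the surgery log CRF: blood-loss band, and any BPA/FVIII for the surgery before discharge (yes/no). Endpoint 1 is loss under 25% and No. Endpoint 2 is met when the blood-loss response "is “25% to <50%” or “>=50%” AND response to “Did the patient use any BPA/*FVIII* for the surgery before the discharge?” is “Yes".

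**The concern.** The two sentences defining endpoint 2 describe different sets of patients. A patient can be Fair or Poor without having received BPA/FVIII, so the conjunction is narrower than the stated measure. SAP 4.4.1 follows the conjunction without saying so, while SAP 2.2.1 still presents the result as a hemostatic rating.

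The study asks whether emicizumab alone controls surgery-related bleeding. Excess bleeding managed without BPA/FVIII and BPA/FVIII given without excess bleeding are different answers to that question. Both fall outside endpoints 1 and 2, and the SAP does not plan to show them separately. A reader who takes the endpoint 2 percentage as the Fair/Poor rate may be misled, and cannot recover the split from the two percentages.

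**Working it through.** **Step 1. The plan's own precision figures.** The exact 95% limits for x events in n patients are

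- lower = Beta⁻¹(0.025; x, n−x+1)
- upper = Beta⁻¹(0.975; x+1, n−x)

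These reproduce all six rows of SAP Table 1 (Protocol Table 5) to three decimals: 2/20 gives 0.012–0.317, 6/20 gives 0.119–0.543, 10/20 gives 0.272–0.728, 3/30 gives 0.021–0.265, 9/30 gives 0.147–0.494 and 15/30 gives 0.313–0.687.

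**Step 2. All combinations of the two CRF items.** Four loss bands by Yes/No give 8 combinations. Two meet endpoint 1, two meet endpoint 2 and four meet neither. They collapse to four cells:

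| Excess loss | BPA/FVIII | SAP 4.4.1 | Appendix 2 scale |
|---|---|---|---|
| under 25% | No | Endpoint 1 | Good/Excellent, if blood component use is as expected |
| ≥25% | Yes | Endpoint 2 | Fair/Poor, unless a loss above 50% is explained by another surgical/medical issue or the dose was planned and nothing further was needed |
| ≥25% | No | Neither | Fair/Poor if blood components or other intervention were needed; no exact level if nothing was needed |
| under 25% | Yes | Neither | No exact level if given for bleeding; could be Good/Excellent if the dose was planned |

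The coding thus differs from the scale in three further ways. It counts any BPA/FVIII, where the scale counts unplanned doses. It has no exclusion for other causes of loss. It has no transfusion term, so endpoint 1 could include a patient who is not Good/Excellent, though this is remote in minor surgery.

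**Step 3. Illustration with assumed counts, n = 20.** Take 17 patients under 25%/No, 1 under 25%/Yes, 1 at ≥25%/No given blood components, and 1 at ≥25%/Yes (17 + 1 + 1 + 1 = 20).

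- Endpoint 1 as coded: 17/20 = 85% (62.1–96.8%).
- Endpoint 2 as coded: 1/20 = 5% (0.1–24.9%).
- Neither: 100% − 85% − 5% = 10%, which is 2/20 and mixes two different outcomes.
- Fair/Poor on the scale: 2/20 = 10% (1.2–31.7%).
- If the under 25%/Yes dose was planned, Good/Excellent: 18/20 = 90% (68.3–98.8%).

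The error can also run the other way. If two patients are ≥25%/Yes and one of them lost more than 50% for a surgical reason, endpoint 2 is 2/20 = 10%, while Fair/Poor is 1/20 = 5%.

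**Step 4. Size per patient.** One patient moves a rate by 100/n points: 5.0 at n = 20 and 3.3 at n = 30. At n = 30, 1/30 = 3.3% (0.1–17.2%) compares with 2/30 = 6.7% (0.8–22.1%). SAP 2.2.3 says the study is being terminated early with limited numbers. At an assumed n = 10 the step is 10 points: 1/10 = 10% (0.3–44.5%) against 2/10 = 20% (2.5–55.6%).

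**Step 5. Does another analysis show the split?** The sensitivity analysis in SAP 4.4.4 covers treated bleeds after discharge only. SAP 4 falls back to listings if data are sparse, but does not say that a listing will show both CRF items. No cross-tabulation or four-level rating table is planned.

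**The case against.** The SAP rule codes exactly the conjunction in the first sentence of endpoint 2, so the conflict starts in the protocol's wording. That is right. It means the endpoint text needs reconciling as well as the coding.

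A ≥25%/No patient fails endpoint 1, so this cell does not inflate the success rate. Nor do the documents call endpoints 1 and 2 complementary. Both points stand: the loss is from the failure percentage only, and a sum below 100% is not in itself an error.

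The safety endpoints in SAP 2.2.5 cover transfusion during surgery, and complications requiring hospitalization or return to surgery. They would show some of the missed patients. They are only a partial backstop, because neither is crossed with blood loss and the transfusion endpoint stops at surgery.

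Transfusion should be rare in the procedures listed in Protocol Appendix 3, and the worked example relies on one. That is fair, and it is why the claim is that endpoint 2 can miss patients. Poor can also be reached through other intervention.

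Planned doses would be departures, since SAP 2 says "BPA/FVIII should only be used for treatment of bleeding", and major deviations are to be listed. The difference between any and unplanned doses is therefore marginal. The reverse example is also limited: a loss above 50% with a surgical cause fits no level on the scale, so the comparison is with an unrated patient.

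If the SAP reported the two CRF items separately, each missing cell would follow by subtracting endpoint 2 from the relevant total. It does not commit to reporting those totals.

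**Conclusion.** The concern holds and should be fixed. The documents name the Fair/Poor rating as the measure of endpoint 2, and the SAP computes something else. Followed exactly, it can leave Fair/Poor patients out of the only pre-discharge failure percentage. It also merges two different outcomes into a remainder whose total can be inferred if no data are missing, but whose split cannot.

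The effect is 5.0 points per patient at n = 20 and 3.3 at n = 30, and larger in a smaller cohort. How many patients are affected is unknown: every count above is assumed, as is n = 10. Not every ≥25%/No patient is Fair or Poor, and errors can run in either direction. The study is descriptive, so the consequence is for the interpretation of the primary results. No test, threshold or sample-size figure changes.

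**What to change.** Settle this before the single analysis after database lock (SAP 2.4).

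- In SAP 2.2.1, reconcile the conjunction with the Fair/Poor measure, and state how the chosen definition relates to Protocol Table 1.
- In SAP 4.4.1, tabulate blood-loss band by BPA/FVIII use for each cohort. Show ≥25%/No and under 25%/Yes as their own rows. Split the latter by reason for use where the Concomitant Medications CRF records it.
- If data are too sparse for a table, state that the listing shows both items for each patient.
- Add one sentence saying that the coded endpoints are not the ISTH rating and naming the differences: any versus unplanned doses, no exclusion for other surgical/medical causes, and no transfusion term.
- Apply the transfusion or intervention criteria, or the four-level rating, only where those data were captured.

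The cost is one table or listing per cohort and a few sentences in the SAP, with no new data and no protocol amendment. The downside is that the reported rates may look less favourable, and in very small cohorts some cells will hold 0 or 1 patients.

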4.4.2 Secondary Efficacy Endpoints

Not applicable.

4.4.3 Exploratory Efficacy Endpoints

As an exploratory efficacy endpoint, the percentage of patients with zero bleeds (regardless of treated or not) after being discharged from surgery will be summarized separately for the inhibitor and non-inhibitor cohorts and will be displayed overall and by surgery type.

